3.3.1 Temozolomide (TMZ) Dose Modifications

Dose modification(s) are based on adverse event occurrence and may be implemented during any treatment cycle (Table 11) or prior to initiation of each new cycle per Table 8. If multiple AEs are seen, the dose administered should be based on the dose reduction required for the most severe grade of any single AE. If TMZ is delayed or discontinued in combination therapy, the Zotiraciclib (TG02) component of treatment may continue, unless there is clear reason to discontinue Zotiraciclib (TG02) simultaneously.

Table 9: TMZ Dose Levels for Modification Table		
Dose Level	DD TMZ Dose, mg/m²/day	MN TMZ Dose, mg/m²/day
-2	80	32
-1	100	40
0	125	50

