3.3.1.2 Dose reductions (Summarized in Table 11)

If any non-hematologic AE observed was grade 3 (except nausea and vomiting) and/or if platelets $< 50 \times 10^9/L$ and/or ANC $< 1 \times 10^9/L$, then the dose should be reduced by one dose level. For patients who would require dose reductions to a dose level < -2 as defined in table 10, temozolomide will be stopped. Also, if any of the same non-hematologic grade 3 AE recurs (except, nausea and vomiting,) after reduction for that AE, then temozolomide will be stopped.

If any treatment-related non-hematologic AE observed was grade 4 (except nausea and vomiting) then adjuvant temozolomide treatment should be stopped.

Any dose reductions of temozolomide will be determined according to (1) non-hematologic AE, as well as (2) the lowest/worst ANC and platelet counts observed. No dose escalation should be attempted. If the dose reduction occurs in the middle of the cycle, the reduced dose should be applied as soon as the treatment resumes (i.e. next dose).

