Table 10: Zotiraciclib (TG 02) Dose Modification Table	
Dose Level	TG 02 (mg/day on days 1, 12, 15, 26 per 28 day cycle)*
-1	150
0	200
1	250
2	300

Summary of Dose Modification or Discontinuation

Table 11: Dose Modifications and Delay*				
	Zotiraciclib (TG02)		TMZ	
Grade	Hematologic**	Non-hematologic	Hematologic**	Non-hematologic
0-1	No dose modification	No dose modification	No dose modification	No dose modification

Table 11: Dose Modifications and Delay*				
	Zotiraciclib (TG02)		TMZ	
2	Hold until resolved to ≤ G1; if persists beyond 4 weeks, dose reduce one level.	Hold until resolved to ≤ grade 1; if > 4 weeks then dose reduce 1 level.	Hold until resolved to ≤ grade 1; if > 4 weeks then dose reduce 1 level.	No dose modifications for non-hematologic AEs (G 0-2), unless the adverse event attributed to Temozolomide.
3	If not recovered to ≤ G2 within 3 days, STOP. If recovered to ≤ G2 within 3 days, re-start @ one dose level lower once recovered to G1 or less.***	Delay up to 4 weeks until ≤ Grade 1. If unresolved after 4 weeks, then stop. If resolved to ≤ grade 1; then dose reduce by 1 level.	Hold until resolved to ≤ grade 1; if > 4 weeks, then stop.	Hold until resolved to ≤ grade 2; if greater than 4 weeks then stop. If less than 4 weeks, reduce by one dose level. If the same non-hematologic grade 3 AE recurs after reduction for that AE, then stop.
4	If not recovered to ≤ G2 within 3 days, STOP. If recovered to ≤ G2 within 3 days, re-start @ one dose level lower once recovered to G1 or less	Stop treatment.	Stop treatment.	Stop treatment.

* If the patient develops a lower extremity deep venous thrombosis and requires anticoagulation or intervention (grade 2 or 3 toxicity), treatment may be restarted after a 2-week rest period if the patient is stably anticoagulated and is judged medically stable to begin chemotherapy. (Please note: DVT is graded in the CTC version 4.0 as grade 1= superficial thrombosis, grade 2= DVT, medical intervention indicated, grade 3= uncomplicated pulmonary embolism, medical intervention indicated, grade 4=life-threatening pulmonary embolism, cerebrovascular event, arterial insufficiency, urgent intervention indicated).

** With the exception of lymphopenia, grade 1-4.

***If G3 neutropenia recovers within 72 hours, the Principal Investigator may consider no dose reduction of Zotiraciclib (TG02).

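### Table 11 omits the temozolomide dose cut that section 3.3.1.2 requires after low neutrophil or platelet counts, and the table cross-references do not supply it

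*Combined protocol and SAP*

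**What the plan says.** Section 3.3.1.2 is headed "Dose reductions (Summarized in Table 11"). For platelets below 50 and/or ANC below 1 (× 10^9/L) it says "then the dose should be reduced by one dose level". The judgement rests on "the lowest/worst ANC and platelet counts observed", and after a mid-cycle reduction "the reduced dose should be applied as soon as the treatment resumes (i.e. next dose").

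In Table 11, printed under section 3.3.2, the grade 3 temozolomide hematologic cell reads "Hold until resolved to ≤ grade 1; if > 4 weeks, then stop".

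Sections 3.3.1 and 3.3.2 divide the work between two tables: Table 8 before each new cycle, Table 11 during a cycle. For temozolomide, the hematologic row of Table 8 and its grade 2 and 3 non-hematologic rows refer onward to Table 9, titled "Table 9: TMZ Dose Levels for Modification Table". Table 9 contains levels 0, -1 and -2 for the two schedules and nothing else.

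For patients who would need to go below level -2, section 3.3.1.2 says "as defined in table 10, temozolomide will be stopped". Table 10 is titled "Table 10: Zotiraciclib (TG 02) Dose Modification Table" and its levels run from -1 to 2.

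**The concern.** A summary table should lead to the same dose as the text it summarises. This one does not do so for neutrophil and platelet counts in the temozolomide column. Because the neighbouring grade 3 cells all state a cut, silence in the remaining cell invites the reading that temozolomide restarts at the same dose. Table 8 does not correct this, since it leads to a list of dose levels with no rule for moving between them.

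Section 3.3.2 expects prolonged myelotoxicity to be attributed mostly to temozolomide, so this column will often decide the dose. Section 13.1.5 describes myelosuppression as the dose-limiting reaction to temozolomide in refractory anaplastic astrocytoma. At stake is a restart at a dose higher than the protocol text sets, after a count low enough to trigger a reduction. In the Phase II control arm, temozolomide is the only study drug before crossover, so no TG02 reduction accompanies a missed cut.

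**Working it through.** The plan gives no figure to reproduce. The check compares the rules cell by cell and then applies the Table 9 doses.

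**Grade 3 row of Table 11**

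| Cell | Cut stated? |
|---|---|
| TG02 hematologic | Yes: restart one level lower if recovered to grade 2 or less within 3 days and then to grade 1 or less (a footnote allows discretion for neutropenia) |
| TG02 non-hematologic | Yes: one level after recovery to grade 1 or less |
| Temozolomide non-hematologic | Yes: one level if recovered within 4 weeks |
| Temozolomide hematologic | No: hold, and stop after 4 weeks |

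The only cut in the temozolomide hematologic column is at grade 2, and only when the event lasts beyond 4 weeks. No cell in that column has a cut triggered by counts. The omission therefore does not depend on how the counts map to CTCAE grades.

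**Worked case.** Take a dose-dense patient at level 0 whose ANC falls to 0.8 × 10^9/L and recovers within 4 weeks.

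- Section 3.3.1.2: 0.8 is below 1, so the dose goes to level -1 when treatment resumes, which is 100 mg/m² per day.
- Table 11, read alone as grade 3: hold until grade 1 or less, with no restart dose given. A reader could resume at 125 mg/m² per day.
- Table 8, if the decision falls at cycle start: go to Table 9, which offers 125, 100 and 80 without saying which applies.

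**Size of one missed cut, dose-dense schedule.** Dosing days per 28-day cycle are 1–7 and 15–21, so 14 days (section 3.2.1.1). Doses are from Table 9.

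- Unreduced: 14 × 125 = 1,750 mg/m².
- Reduced: 14 × 100 = 1,400 mg/m².
- Difference: 1,750 − 1,400 = 350 mg/m²; ratio 1,750 / 1,400 = 1.25, or 25% above the dose in 3.3.1.2.
- If only the second block of a cycle is affected: 7 × 125 = 875 against 7 × 100 = 700 mg/m², a difference of 175.

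Dose-dense is the relevant schedule from here on: section 10.1 names it the winner for Phase II, and section 3.2.1.3 enrols the remaining Phase I cohort to Arm 1 only.

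**The case against.** The strongest reply is that the rule is already in the protocol. Section 3.3.1.2 gives the trigger, the size of the cut, the worst-count basis and the timing, and section 3.3.2 sends myelotoxicity attributed to temozolomide back to section 3.3.1. The Table 11 cell does not say to resume at the same dose. A careful reader can combine the two: hold, then reduce. This stands. A reader might infer that text and table contradict each other, or that staff would restart at full dose; the documents support only that they could.

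Second, the opening of section 3.3 lets the principal investigator reduce one drug first when both would need a cut. In the combination arm, an unreduced temozolomide restart after a TG02 cut may therefore be permitted. This also stands, and it qualifies the 25% figure. The Table 11 footnote on grade 3 neutropenia that recovers within 72 hours likewise makes the TG02 cut discretionary. Neither provision supplies the missing temozolomide rule.

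Third, a reader might take the moderate to severe neutropenia in the first 16 Phase I patients (section 1.2.2.2) as a measure of how often the missing clause would apply. It is not. That sentence appears under TG02 risks, and section 1.2.7 describes neutropenia with rapid onset and recovery, in one case within 24 hours of a TG02 dose, for which marrow dysfunction is thought unlikely. Nor does anything in the documents show an effect on the PFS comparison.

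Finally, the Table 10 reference can be called a slip that the table titles expose. That is fair, but it occurs in the one passage that holds the full rule.

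**Conclusion.** The point holds as an inconsistency between section 3.3.1.2 and the tables meant to put it into practice. Both tables assigned to dosing decisions fail to carry the count-triggered temozolomide cut, and the text that does carry it refers to the wrong table for its floor. It should be corrected, but it is not a missing rule or a design flaw.

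The consequence is conditional. If Table 11 is used without 3.3.1.2, and the discretion in section 3.3 is not being exercised, one missed cut gives the 350 mg/m² per-cycle excess shown above. How often this would happen is not estimated.

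One assumption applies to the row concerned: ANC below 1 and platelets below 50 × 10^9/L are taken as grade 3 or worse. The documents do not print the CTCAE version 4.0 grade 3 cut-offs; section 13.1.5 prints only grade 4 values (ANC below 500 and platelets below 20,000 cells/μL). Grade 4 counts, for which Table 11 says stop, are outside this point.

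**What to change.** (a) In the grade 3 temozolomide hematologic cell of Table 11 add: *if recovered to ≤ grade 1 within 4 weeks, restart one dose level lower if the worst count was ANC < 1 or platelets < 50 × 10^9/L (3.3.1.2)*. Tying the clause to these counts avoids a temozolomide cut for grade 3 anemia or isolated leukopenia.

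(b) In the temozolomide entries of Table 8, refer to 3.3.1.1 and 3.3.1.2 for the delay, stop and reduction rules, and to Table 9 for dose levels only. Leave the non-hematologic rule as worded.

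(c) In 3.3.1.2, change the reference to Table 10 into Table 9.

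If the sponsor in fact intends no cut after a grade 3 count that recovers, 3.3.1.2 is the text to amend instead. Either way the cost is a protocol wording change. Sample size, visits and data collection stay as they are.

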3.3.3 Pre-medications

3.3.3.1 Zotiraciclib (TG02)

Patients must receive vigorous prophylactic treatment for nausea and vomiting. Prophylactic use of moderately anti-emetogenic treatments (e.g., 5-HT₃ antagonist) has been more effective at controlling nausea and vomiting than lightly anti-emetogenic treatments or treatment after onset.

3.3.3.1.1 Prophylaxis for Nausea/Vomiting

Zotiraciclib (TG02) is potentially highly emetogenic. Vigorous anti-emetic prophylaxis is required prior to administration of Zotiraciclib (TG02) and should continue at least 24 hours after Zotiraciclib (TG02) administration or until nausea/vomiting returns to Grade 0 or 1. Anti-emetic prophylaxis is also highly recommended to be started on the day prior to Zotiraciclib (TG02) administration.

Some recommended prophylaxis regimens include but is not limited to the following:

- 5-HT₃ antagonist (e.g., ondansetron, granisetron, palonosetron, etc.)
- 2.5 mg olanzapine or
- other moderate anti-emetic regimens tailored to the individual patient at the Investigator's discretion

3.3.3.1.2 Prophylaxis for Diarrhea

Due to frequent reports of diarrhea with Zotiraciclib (TG02) administration, vigorous anti-diarrheal prophylaxis (e.g., loperamide or equivalent) is required prior to administration of Zotiraciclib (TG02) and should continue at least 24 hours after Zotiraciclib (TG02) administration or until diarrhea returns to Grade 0 or 1.

The recommended prophylaxis includes but is not limited to the following:

- a. Loperamide the day prior to and the day of Zotiraciclib (TG02). Suggest that if patient had diarrhea on day of Zotiraciclib (TG02) that Loperamide 2-4mg is administered following first loose stool on day after Zotiraciclib (TG02) and after each stool if an hour as elapsed since last dose, as needed thereafter.
- b. Once diarrhea has occurred, Loperamide 4mg after first loose stool, and Loperamide 4mg after the second and third stool respectively, with patient to call the study team practitioner after third loose stool.
- c. Consider Lomotil and Tincture of Opium, if diarrhea continues. A nutrition consult may also be beneficial for potential diet modifications.

3.4 QUESTIONNAIRES

3.4.1 MD Anderson Symptom Inventory-Brain Tumor (MDASI-BT):

The MDASI-BT will be administered at baseline and at the time of imaging analysis as outlined in the protocol. Of note, every attempt should be made to administer the MDASI-BT prior to informing the patients about the results of the imaging study. The MDASI-BT will be completed only by the patient, unless changes in vision or weakness make this difficult. If this occurs, then the caregiver or research assistant may read the questions to the patient or assist with marking the severity number or score as described by the patient. A caregiver may complete the questionnaires as a patient proxy if the patient's deficits preclude self-report; however, this must be done at every assessment from baseline to end of treatment. In addition, information regarding demographics and treatment history will be collected as part of the larger study and used in this analysis.

The MDASI-BT consist of symptoms rated on an 11-point scale (0 to 10) to indicate the presence and severity of the symptom, with 0 being "not present" and 10 being "as bad as you can imagine." Each symptom is rated at its worst in the last 24 hours. Symptoms included on the instrument include those commonly associated with cancer therapies, and those associated with the underlying disease. The questionnaire also includes ratings of how much symptoms interfered with different aspects of a patient's life in the last 24 hours. These interference items include: general activity, mood, work (includes both work outside the home and housework), relations with other people, walking, and enjoyment of life. The interference items are also measured on 0 - 10 scales. The average time to complete this instrument is 5 minutes. The MDASI-BT has been translated into multiple languages, but the English language version will be used for this study[44].

3.4.2 PRO-CTCAE*:

Patients will complete a baseline PRO-CTCAE any time after enrollment but before starting treatment, and again on days 2, 8, 14, 21, and 28 in each treatment cycle, if the patient is able. There are 13 questions in total. The questions are focused on 12 symptoms that are commonly reported by the patients taking Zotiraciclib (TG02). It takes 5-10 minutes to complete the questionnaire. It will only be completed by the patient, unless changes in vision or weakness make this difficult. If this occurs, then the caregiver may read the questions to the patient or assist with marking the answers as described by the patient. A patient caregiver may complete the questionnaires as a patient-preference proxy if the patient's deficits preclude self-report. The questionnaires are allowed to be completed within +/-2 days from the scheduled dates. The PRO-CTCAE is only going to be conducted in the cohort expansion part of the study. Patients will complete at least 2 questionnaires per cycle.

*The PRO-CTCAE will not be performed in the Post Interim Analysis cohort.

3.5 ASSESSMENTS WHILE ON STUDY THERAPY

3.5.1 Cycle 1 Assessments

During the 2nd week of treatment (i.e. 28-day cycle), the patient will have a complete blood count (CBC) with differential and platelet count. In phase I study, if grade 3 neutropenia is identified, repeat CBC with differential every 3 days until it improves to \leq grade 2. Patient may have CBC drawn at NIH lab or outside community lab.

During the 4th week of treatment (i.e. 28-day cycle), the patient will have the following assessments:

- Physical exam with vital signs, neurological exam, neurological function score and neurological examination (including documentation of the patient's Karnofsky Performance Status), mental status score. Weight is also included. Toxicity monitoring.
- A complete blood count (CBC) with differential and platelet count. In phase I study, if grade 3 neutropenia is identified, repeat CBC with differential every 3 days until it improves to \leq grade 2.
- PT, PTT, INR, total protein, albumin, calcium, phosphorus, magnesium, glucose, BUN, creatinine, sodium, potassium, total bilirubin, alkaline phosphatase, LDH, SGPT (ALT), SGOT (AST) and a pregnancy test for women of childbearing potential
- 12-lead EKG.

On days 2, 8, 14, 21, and 28, patients will complete PRO-CTCAE form. (+/- 2 days).

The PRO-CTCAE will not be performed in the Post Interim Analysis cohort.

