3.5.2 Cycle 2 Assessments

During the 2nd week of treatment, the patient will have a complete blood count (CBC) with differential and platelet count. In phase I study, if grade 3 neutropenia is identified, repeat CBC with differential every 3 days until it improves to \leq grade 2. Patient may have CBC drawn at NIH lab or outside community lab.

During the 4th week of treatment (i.e. 28-day cycle), the patient will have the following assessments:

- Physical exam with vital signs, neurological exam, neurological function score and neurological examination (including documentation of the patient's Karnofsky Performance Status), mental status score. Weight is also included.
- A Gd-DPTA enhanced MRI, with DWI, ADC, SWI, FLAIR, perfusion, dynamic contrast enhanced and dynamic susceptibility contrast sequences should be performed.
- MD Anderson Symptom Inventory-Brain Tumor Module (MDASI-BT). If the MDASI-BT is completed by the patient for Natural History study within 14 days from the MRI assessment, it can be used but only if it was administered prior to informing patient of tumor imaging results.
- Toxicity monitoring

- A complete blood count (CBC) with differential and platelet count every two weeks. In phase I study, if grade 3 neutropenia is identified, repeat CBC with differential every 3 days until it improves to \leq grade 2.
- PT, PTT, INR, total protein, albumin, calcium, phosphorus, magnesium, glucose, BUN, creatinine, sodium, potassium, total bilirubin, alkaline phosphatase, LDH, SGPT (ALT), SGOT (AST) and a pregnancy test for women of childbearing potential
- 12-lead EKG.
- Response evaluation.

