3.5.3 Subsequent cycles

For all subsequent odd-numbered cycles (i.e. cycle 3, 5, 7, 9, 11), patients will repeat assessments outlined in section **3.5.1**

For all subsequent even-numbered cycles (i.e. cycle 4, 6, 8, 10, 12), patients will repeat assessments outlined section **3.5.2**.

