3.8 STUDY CALENDAR

Procedure	Screening/ Baseline	Cycle 1				Cycle 2				Subsequent Odd numbered cycles		Subsequent Even numbered cycles		Off- study visit ⁸
		Wk 1	Wk 2*	Wk 3	Wk 4*	Wk 1	Wk 2*	Wk 3	Wk 4*	Wk 2*	Wk 4*	Wk 2*	Wk 4*	
Informed Consent	X													
Medical History	X													
Physical Exam ¹	X				X ¹				X ¹		X ¹		X ¹	X ¹
MDASI-BT	X								X				X ⁷	
ProCTCAE***	X	X	X	X	X	X	X	X	X	X	X	X	X	
GD-DPTA MRI of brain	X								X				X ⁶	
Hematology ²	X		X		X		X		X	X	X	X	X	X
Chemistry ³	X				X				X		X		X	X
PT/PTT/INR	X				X				X		X		X	
12-lead EKG	X				X				X				X	
Pregnancy Test ⁴	X				X				X		X		X	X
Tumor Pathology	X													
Paraffin Tissue block ⁵	X													
Response evaluation									X				X	
Research samples (PK, PG, neutrophil) ^{9,10}		X ^{9,10}												

1. Physical examination includes vital signs, neurological exam, neurological function score, Karnofsky performance score, mental status score. Height and weight are also included. **Height measured only at baseline.**
2. Includes CBC with differential and platelets. In phase I study, once grade 3 neutropenia is identified, CBC with differential will be tested every 3 days until it improves to \leq grade 2.
3. Includes: Total protein, albumin, Ca, Mg, P, glucose, BUN, creatinine, Na, K, total bilirubin, alkaline phosphatase, LDH, SGPT (ALT), SGOT (AST).
4. Only for women of childbearing potential as defined in section 15.2. To be performed before each new cycle of therapy.
5. If a tissue block is unavailable, unstained slides are acceptable.
6. Brain MRI w/wo contrast needs to be done every two cycles of treatment.
7. MDASI-BT questionnaire needs to be completed at imaging cycles within +/- 1week. (prior to imaging results having been discussed with the patient). If the MDASI-BT is completed by the patient for Natural History study (CC 16C0151) within 14 days from the MRI assessment, it can be used but only if it was administered prior to informing patient of tumor imaging results.
8. If patient does not return for 30-day safety visit, patient will be taken off study for reason listed in section 3.10.3 If patient does not return, physical exam and blood work is not mandatory.

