9. On cycle 1 day -3, collect following samples from patients in the **Phase 1 cohort expansion only**: PK studies (1 6mL green sodium heparin tube at following timepoints-pre-dose, 1hr, 2hr, 4hr, 12hr, 24hr, 48hr, and 72hr post-oral dose); PG studies (1 purple tube EDTA, 6mL, pre-dose) and neutrophil analysis (2 additional purple top EDTA, 6mL each for CBC/diff and neutrophil marker; and 1 additional heparinized green top tube, 6 mL for plasma isolation for monitoring neutrophil activation markers) at following timepoints- pre-dose, 1hr, 2hr, 4hr, 12hr, 24hr, 48hr, and 72hr post-oral dose). All effort will be made to collect samples at prescribed time points; missed timepoints or collections outside the window will be documented but not constitute a deviation.
10. Research sample will be collected for PK/PG study from patients enrolled to the **Post-Interim Analysis cohort** at the following timepoints: pre-dose, 1hr, 2hr, 4hr, 24hr, and 48hr post-oral dose. This will avoid the requirement for inpatient admission. The neutrophil sample will not be collected.
*+/- 3 business days

** Allowance for scheduling changes: Brief interruption and delay in the 28-day cycle may occasionally be required due to travel delays, airport closure, inclement weather, family responsibilities, security alerts and government holidays, etc. This can also extend to complications of disease not attributable to disease progression or protocol therapy. These delays will not be considered protocol deviation. However, any interruption more than 14 calendar days will not be permitted.

*** on days 2, 8, 14, 21, and 28 (+/- 2 days). The ProCTCAE data will not be collected from patients enrolled to the post-interim analysis cohort.

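### The 3-day TG02 stop-or-restart rule in Table 11 applies in Phase II, but the repeat CBC that informs it is required only in Phase I and only for neutropenia

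*Combined protocol and SAP*

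**What the plan says.** **The decision rule.** In Table 11 the TG02 haematologic column reads, for both grade 3 and grade 4: "If not recovered to ≤ G2 within 3 days, STOP". If recovery does come in time, the instruction is to "re-start @ one dose level lower once recovered to G1 or less". A footnote excludes lymphopenia, so neutrophils, platelets and haemoglobin are all covered. A further footnote allows the Principal Investigator to forgo the reduction when grade 3 neutropenia recovers within 72 hours. Section 3.3.2 identifies Table 11 as the within-cycle table and names the Phase II component among the settings it covers. Nothing in the table limits it to one phase.

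**The count that informs it.** Section 3.5.1 states: "In phase I study, if grade 3 neutropenia is identified, repeat CBC with differential every 3 days until it improves to" grade 2 or less. Section 3.5.2 repeats this. Footnote 2 of the Study Calendar (Section 3.8) agrees: "In phase I study, once grade 3 neutropenia is identified, CBC with differential will be tested every 3 days". Section 3.5.3 carries it into later cycles, where "patients will repeat assessments outlined in section" 3.5.1 (odd cycles) or 3.5.2 (even cycles).

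**What Phase II has instead.** Routine counts fall in weeks 2 and 4 (Section 3.5.2: "A complete blood count (CBC) with differential and platelet count every two weeks"), with a visit window of plus or minus "3 business days". Section 3.3.1.1 adds a check within 72 hours before day 1 of each cycle. Section 6.1 requires adverse events to be followed to baseline or stabilization, with no interval given.

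**The concern.** A rule that turns on recovery within 3 days needs a count by day 3. For Phase II, and in either phase for thrombocytopenia or anaemia, no such count is required. A later count can show that the patient has recovered but not when, so it cannot settle whether TG02 should have been stopped, restarted one level lower, or restarted at full dose under the waiver.

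The protocol recognises the problem. Section 1.2.7 reports that low neutrophil counts mostly recovered within 24-48 hours, including one grade 4 case that was grade 1 a day later. It warns both of premature discontinuation and of risk to patients if follow-up tests are poorly timed.

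At stake is avoidable loss of TG02, or of TG02 dose, in the arm under test. The margin is thin at dose level 0, which Section 10.1 may select for Phase II, because Section 3.3.2 allows only one reduction from that level. An unnecessary reduction would use it up. A timely repeat also helps attribution: Section 3.3.2 expects prolonged myelotoxicity to be assigned to TMZ, and one late count cannot separate prolonged from transient.

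**Working it through.** The plan gives no figure to reproduce. The check sets the rule against the schedule and counts days.

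**Inputs.** Routine counts in weeks 2 and 4 (Sections 3.5.1, 3.5.2, 3.8), taken here as days 8-14 and 22-28. TG02 on days 1, 12, 15 and 26 of a 28-day cycle (Table 7), so the next day 1 is day 29. Decision limit 3 days (Table 11). Day-1 check within the prior 72 hours (Section 3.3.1.1), so days 26-29.

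**Step 1: scope.**

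| | Phase | Toxicity |
|---|---|---|
| Table 11 rule for TG02 | I and II | any grade 3-4 haematologic except lymphopenia |
| Repeat CBC every 3 days | I only | neutropenia only (the text names grade 3) |

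The rule is wider than the monitoring on both counts.

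**Step 2: gap between routine counts.** Shortest 22 − 14 = 8 days; longest 28 − 8 = 20 days. None of the 7 × 7 = 49 day pairs is 3 days apart or less. If both visits may move by 3 calendar days (days 5-17 and 19-31), the gap runs from 19 − 17 = 2 to 31 − 5 = 26 days, and 3 of 13 × 13 = 169 pairs are within 3 days: (16, 19), (17, 19) and (17, 20). If the business-day window spans a weekend (plus or minus 5 calendar days), it is 15 of 283 ordered pairs. These are counts of day pairs, not probabilities.

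**Step 3: week 4 to the day-1 check.** Of 22 ordered pairs (count on days 22-28, later check on days 26-29), 12 are within 3 days. The gap is weaker at the end of the cycle.

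**Step 4: next TG02 dosing day after a routine count.**

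| Week-2 count on day | 8 | 9 | 10 | 11 | 12 | 13 | 14 |
|---|---|---|---|---|---|---|---|
| Next dose day | 12 | 12 | 12 | 12 | 15 | 15 | 15 |
| Days to it | 4 | 3 | 2 | 1 | 3 | 2 | 1 |

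| Week-4 count on day | 22 | 23 | 24 | 25 | 26 | 27 | 28 |
|---|---|---|---|---|---|---|---|
| Next dose day | 26 | 26 | 26 | 26 | 29 | 29 | 29 |
| Days to it | 4 | 3 | 2 | 1 | 3 | 2 | 1 |

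On 6 + 6 = 12 of 14 nominal draw days a dosing decision falls within the 3-day limit. It may prompt a repeat but does not require one, because a site can hold the dose and wait.

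**Step 5: a constructed case.** Grade 3 neutropenia on day 13; the day-15 dose is held; the next required count, on day 22, is grade 1. The limit was day 13 + 3 = day 16, and the evidence arrives 22 − 16 = 6 days later. If the neutrophils had recovered by day 15, as Section 1.2.7 would suggest, the patient qualified for restart and possibly for the waiver. Nothing on record shows it.

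**The case against.** The strongest reply is that the rule carries its own monitoring need: nobody can apply a 3-day test without looking by day 3, calendar visits are minimums, and community-laboratory counts are already allowed. Dosing days reinforce this, since TG02 cannot be given again without a count and one is usually due within 3 days. This stands in part. The gap between routine counts overstates how long a site would normally wait. But a prompt is not a requirement, and the sponsor thought the requirement worth writing for Phase I.

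Three stronger readings are tempting and are not supported:

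- A reader might infer that Phase II patients could be re-dosed with TG02 while still cytopenic. Table 11 requires grade 1 or less before restart.
- A reader might infer that the plan permits restart after late recovery. That would be a deviation from Table 11.
- A reader might infer that the progression-free survival comparison is compromised. The documents give no episode rate and no link from this gap to the primary analysis.

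Other limits also stand. The 3-day rule is only in the TG02 columns, so it does not touch control patients while on TMZ alone. Myelotoxicity attributed to TMZ falls under a column with no 3-day test. Section 1.2.7 describes neutropenia, mostly without falls in platelets or haemoglobin, so the evidence of rapid recovery is specific to neutrophils. Platelets and haemoglobin belong in the fix because Table 11 applies the same test to them. Finally, Phase II has not opened in this version, and the 12 further Phase I patients already have the neutropenia repeat.

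**Conclusion.** The mismatch is real and lies between two explicit rules: the TG02 rule reaches Phase II and all non-lymphocyte cytopenias, while the timed repeat stops at Phase I and neutropenia. Following the plan exactly can leave a Phase II site without the count its dose rule depends on. The consequence is possible avoidable discontinuation of TG02, or an unnecessary reduction, after a transient episode.

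Its size is modest and uncertain. Routine counts are nominally 8 to 20 days apart, but a dosing day falls within 3 days of 12 of 14 nominal draw days and will often prompt a repeat. How often it would not, and how many patients that would affect, cannot be estimated from the documents. The day counts assume week 2 is days 8-14 and week 4 is days 22-28, with visits at their nominal times unless a window is stated. This is a cheap improvement to make before Phase II opens.

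**What to change.** In Sections 3.5.1 and 3.5.2 and in footnote 2 of the Study Calendar, remove the Phase I limit and the neutropenia-only trigger. Suggested wording:

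*For any patient receiving TG02, in Phase I or Phase II and including control patients who have crossed over, grade 3 or 4 neutropenia, thrombocytopenia or anaemia requires a repeat CBC with differential by 72 hours, then every 3 days until grade 2 or less. A count confirming grade 1 or less is required before TG02 restarts.*

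Section 3.5.3 then carries this into later cycles unaided. Leave the dose rules and the DLT definitions unchanged.

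The cost is a few extra CBCs per affected patient, which can be drawn at a community laboratory. An episode that resolves in 24-48 hours needs 1 repeat at the 3-day interval (2/3 rounded up). As an upper illustration, an episode lasting the 14 days that Section 13.1.5 gives as the average limit for TMZ counts to return to normal needs about 5 (14/3 rounded up). Fewer 3-day repeats are needed if grade 2 is reached sooner, and one more count may be needed to confirm grade 1. Those potentially covered are up to 40 patients in the Phase II TG02 arm, up to 40 controls if all cross over, and the 12 further Phase I patients. Total draws cannot be estimated without an episode rate.
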